9.4.2 Identity of Investigational Products

Eribulin mesylate will be supplied by the sponsor in labeled containers.

9.4.2.1 Chemical Name, Structural Formula of Eribulin Mesylate

- Test drug code: E7389
- Generic name: Eribulin Mesylate
- Chemical name (IUPAC): 11,15:18,21:24,28-Triepoxy-7,9-ethano-12,15-methano-9*H*,15*H*-furo[3,2-*i*] furo[2',3':5,6]pyrano[4,3-*b*][1,4]dioxacyclopentacosin-5(4*H*)-one, 2-[(2*S*)-3-amino-2-hydroxypropyl]hexacosahydro-3-methoxy-26-methyl-20,27-bis(methylene)-,(2*R*,3*R*,3*aS*,7*R*,8*aS*,9*S*,10*aR*,11*S*,12*R*,13*aR*,13*bS*,15*S*,18*S*,21*S*,24*S*,26*R*,28*R*,29*aS*)-, methanesulfonate (salt)
- Molecular formula: C₄₁H₆₃NO₁₄S (C₄₀H₅₉NO₁₁ · CH₄O₃S)
- Molecular weight: 826.0
- Structural formula:

9.4.2.2 Labeling for Study Drug

Eribulin mesylate will be labeled in accordance with text that is in full regulatory compliance with each participating country and is translated into the required language(s) for each of those countries.

9.4.2.3 Storage Conditions

Study drug will be stored in accordance with the labeled storage conditions. Temperature monitoring is required at the storage location to ensure that the study drug is maintained within an established temperature range. The investigator or designee (or if regionally required, the head of the medical institution) is responsible for ensuring that the temperature is monitored throughout the total duration of the study and that records are maintained; the temperature should be monitored continuously by using either an in-house validated data

acquisition system, a mechanical recording device, such as a calibrated chart recorder, or by manual means, such that minimum and maximum thermometric values over a specific time period can be recorded and retrieved as required.

9.4.3 Method of Assigning Subjects to Treatment Groups

The subjects will receive eribulin mesylate only.

9.4.4 Selection of Doses in the Study

Eribulin mesylate will be administered at the RP2D (1.4 mg/m²; Eisai Study E7389-A001-113). Further information on dose modification is provided in [Section 9.4.1](#).

9.4.5 Selection and Timing of Dose for Each Subject

Eribulin mesylate should be administered by IV infusion over 2-5 minutes on Days 1 and 8 of a 21-day cycle. Eribulin may be diluted in up to 100 mL 0.9% sodium chloride, and administered as an IV infusion over 15 minutes (maximum infusion duration), where clinically appropriate.

9.4.6 Prior and Concomitant Therapy

All prior medications (including over-the-counter medications) administered 30 days before the first dose of study drug and any concomitant therapy administered to the subject during the course of the study (starting at the date of informed consent) until 28 days after the final dose of study drug will be recorded. Additionally, all diagnostic, therapeutic, or surgical procedures relating to malignancy should be recorded. Any medication that is considered necessary for the subject's health and that is not expected to interfere with the evaluation of or interact with eribulin may be continued during the study.

Supportive care will be allowed as per institutional guidelines. Growth factors that support platelet or white blood cell number or function can only be administered in accordance with dose modification guidelines or for culture proven bacteremia or invasive fungal infection. Prophylactic granulocyte colony-stimulating factor should NOT be administered in Cycle 1.

Subjects should not receive any other anticancer therapy (including chemotherapy, radiation therapy, immunotherapy or biologic therapy) or investigational agents while receiving study drug. If these therapies are administered, the subject will be removed from the study. From week 24, the subject may receive radiotherapy for local control and continue to receive drug on study.

9.4.6.1 Drug-Drug Interactions

9.4.6.1.1 ERIBULIN MESYLATE

In adults, no drug-drug interactions are expected with CYP3A4 inhibitors, CYP3A4 inducers or P-glycoprotein (P-gp) inhibitors. Clinically meaningful differences in exposure (AUC)

were not observed in patients with advanced solid tumors when Halaven was administered with or without ketoconazole (a strong inhibitor of CYP3A4 and a P-gp inhibitor) and when Halaven was administered with or without rifampin (a CYP3A4 inducer). Eribulin does not inhibit CYP1A2, CYP2C9, CYP2C19, CYP2D6, CYP2E1 or CYP3A4 enzymes or induce CYP1A2, CYP2C9, CYP2C19 or CYP3A4 enzymes at relevant clinical concentrations. Eribulin is not expected to alter the plasma concentrations of drugs that are substrates of these enzymes ([Halaven USPI, 2016](#)).

Currently, drug-drug interactions of eribulin mesylate have not been studied in children, therefore pediatric subjects taking medications that are strong CYP3A4 inducers (eg, phenytoin, carbamazepine, rifampin, rifabutin, rifapentine, phenobarbital, St. John's Wort) or inhibitors (eg, ketoconazole, itraconazole, clarithromycin, atazanavir, nefazodone, saquinavir, telithromycin, ritonavir, indinavir, nelfinavir, voriconazole) or taking nutritional supplements known to inhibit CYP3A4, will be excluded from the study.

Please refer to <http://medicine.iupui.edu/flockhart/table.htm> for the most current information.

9.4.6.2 Prohibited Concomitant Therapies and Drugs

Subjects should not receive other antitumor therapies while on study. If subjects receive additional antitumor therapies, such as chemotherapy, hormone therapy, palliative radiotherapy (up to week 24), or immunotherapy, this will be judged to represent evidence of disease progression, and study medication will be discontinued. These subjects should complete all off-treatment assessments and continue to be followed for survival in the Follow-Up Period.

Details of other prohibited concomitant therapies and drugs are provided in [Section 9.3.2](#) (Exclusion criterion #2).

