9.5.1.3.2 SECONDARY

Efficacy will also be evaluated according to a secondary endpoint (PFS; defined as the time from the date of the first dose of study treatment until the date of first documentation of progressive disease (PD) or date of death [whichever occurs first]). Assessments for these endpoints are to be performed every 6 weeks by use of consistent imaging methodology (ie, CT scan/MRI or bone scan) and consistent use or nonuse of contrast media) until Week 24, then every 9 weeks. In addition, OS status (disposition) and DOR will be assessed throughout the study. For subjects receiving radiotherapy and/or surgery for local control post week 24, progression will be assessed as the date of radiotherapy/surgical procedure.

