7 CHANGES IN THE PLANNED ANALYSES

Not applicable.

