8 DEFINITIONS AND CONVENTIONS FOR DATA HANDLING

Censoring Rules for PFS/DOR

The PFS censoring rules in this SAP and definition of progression date follow the Food and Drug Administration (FDA) “Guidance for Industry Clinical Trial Endpoints for the Approval of Cancer Drugs and Biologics (2007)”.

Table 1 Censoring Rules for Progression-free Survival Endpoint

Situation	End Date	Censored
Investigator documented PD	Date of the first assessment of the series of radiologic tests that determined PD	No
Death during the study before first PD	Date of death	No
No baseline or post-baseline tumor assessments	Date of first dose	Yes
No progression and no death at the time of data cutoff	Date of last adequate tumor assessment* prior to data cutoff	Yes
Non-study anticancer treatment initiated before progression or death	Date of last adequate tumor assessment* prior to or on date of non-study anticancer treatment	Yes
Death or progression after more than one missed tumor assessments**	Date of last adequate tumor assessment* prior to missed tumor assessments	Yes

PD = progressive disease.

* Adequate tumor assessment is radiologic assessment of CR, PR, SD, non-CR/non-PD or PD as determined by investigators at regular interval as defined in the protocol. Any tumor assessments after new anticancer treatment starts will be removed in the definition of PFS.

**More than one missed visit/adequate tumor assessment is defined as having the duration between the last adequate tumor assessment and PD or death being longer than the gap limit.

a) The gap from baseline to the 1st assessment post-baseline (calculated from C1D1), gap limit = 2*6 weeks + 2*3 Days = 90 days.

- b) The gap from the 1st assessment post-baseline, or from any later assessment -- call it "previous assessment", to the next assessment.
- if Study Day of the previous assessment < (18 weeks - 3 days), then gap limit = 2*6 weeks + 2*3 days = 90 days;
 - if (18 weeks - 3 days) <= Study Day of the previous assessment < 24 weeks - 3 days, then gap limit = 6 weeks + 9 weeks + 2*3 days = 111 days;
 - if Study Day of the previous assessment >= 24 weeks - 3 days, the gap limit = 2*9 weeks + 2*3 days = 132 days.

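### The protocol treats other antitumor therapy given on study as evidence of progression, but SAP Table 1 censors it at an earlier scan without declaring a change; PFS and DOR medians are expected to be longer or unchanged under the SAP rule

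*Protocol*

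**What the plan says.** **Protocol.** Section 9.4.6.2 covers additional antitumor therapies "such as chemotherapy, hormone therapy, palliative radiotherapy (up to week 24), or immunotherapy" received while on study. It says of such therapy that "this will be judged to represent evidence of disease progression, and study medication will be discontinued". It gives no date for the progression.

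Section 9.5.1.3.2, which describes PFS among the efficacy assessments, applies similar logic to a later situation and does give a date: "For subjects receiving radiotherapy and/or surgery for local control post week 24, progression will be assessed as the date of radiotherapy/surgical procedure".

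**SAP.** Section 8, headed as covering PFS and DOR, says that its PFS rules follow the FDA's 2007 guidance on cancer endpoints. Table 1 then provides:
- A progression event is dated at the "Date of the first assessment of the series of radiologic tests that determined PD".
- The situation "Non-study anticancer treatment initiated before progression or death" is marked as censored, at the last adequate tumor assessment "prior to or on date of non-study anticancer treatment".
- A footnote adds: "Any tumor assessments after new anticancer treatment starts will be removed in the definition of PFS".

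No row counts new therapy, or local-control treatment after Week 24, as progression. SAP 5.4.2 points to section 8 for the censoring of both endpoints. SAP section 7, on changes in the planned analyses, reads "Not applicable".

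**The concern.** The same subject can be a progression under the protocol and a non-event, at an earlier date, under the SAP. Once censored, the subject cannot become an event later: scans after the new therapy are excluded, the row also takes precedence over a later death, and off-treatment scanning stops when another anticancer therapy starts (Protocol 9.3.3 and 9.5.1.4). The rule alone therefore decides these subjects' outcome.

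PFS is the first-listed secondary objective, and Protocol 9.2 calls it an appropriate surrogate endpoint. DOR follows the same rules and rests on responders only, so each reclassified subject weighs more. Someone who reads the protocol and then sees no declared change in the SAP would assume that the protocol's rule was applied.

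**Working it through.** The documents state no expected PFS, event count or rate of new therapy, so the plan has no figure of its own to reproduce. Every size below rests on an assumption. From the documents come N = 45, scans every 6 weeks to Week 24 and then every 9 weeks, and Kaplan-Meier medians for all cohorts combined.

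**1. Direction.** Suppose n subjects are at risk just after a scan, one of them then starts new therapy, and j others have events between that scan and the therapy date. Just after the therapy date the Kaplan-Meier factor is:
- protocol rule: (n - 1 - j)/n
- SAP rule: (n - 1 - j)/(n - 1)

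The SAP curve is higher from that date on, by the ratio n/(n - 1). Between the scan and the therapy date the factors are (n - j)/n and (n - 1 - j)/(n - 1), so if j is at least 1 the SAP curve is briefly lower. Longer or unchanged is thus the expected direction for the median, not a certainty in every sample.

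**2. Size under constant, independent hazards.** Let h1 be the hazard of documented progression or death, h2 the hazard of new therapy, and f = h2/(h1 + h2).
- Protocol-rule median: ln2/(h1 + h2)
- SAP-rule median: ln2/h1
- Ratio: (h1 + h2)/h1 = 1/(1 - f)

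At f = 10% the ratio is 1/0.90 = 1.11; if all 45 subjects have a first event, that is 0.10 × 45 = 4.5 subjects. At f = 20% it is 1/0.80 = 1.25, or 9 subjects. The formula ignores the scan grid.

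**3. Worked example on the scan grid (assumed data).** Of 45 subjects, 20 progress at Week 6, 25 remain, and 12 of these fail by Week 12, leaving 13. Of the 12, k start new therapy at Week 9 and the rest progress at the Week 12 scan.
- 12-week PFS, protocol rule: 13/45 = 28.9% for every k
- 12-week PFS, SAP rule: (25/45) × 13/(25 - k)

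| k | 12-week PFS, protocol | 12-week PFS, SAP | Median, protocol | Median, SAP |
|---|---|---|---|---|
| 2 | 28.9% | 31.4% | 12 weeks | 12 weeks |
| 5 | 28.9% | 36.1% | 9 weeks | 12 weeks |
| 9 | 28.9% | 45.1% | 9 weeks | 12 weeks |

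Under the protocol rule the curve after Week 9 stands at (25 - k)/45, which is 51.1% for k = 2 and 44.4% for k = 5. That is why the median moves in one case and not in the other.

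**4. Simulation.** N = 45, 2000 runs per scenario, the 6/9-week scan schedule, assumed true medians of 6, 10 and 14 weeks.

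| Share starting new therapy | Runs with longer SAP median | Excess in 24-week PFS under SAP rule |
|---|---|---|
| about 4% | 9% to 15% | about 0.5 to 1 point |
| about 17% to 20% | 43% to 60% | about 2 to 6 points |

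In the remaining runs the medians were equal; essentially none were shorter. With 6 responders, standing in for DOR, and about 11% or 27% starting new therapy, the SAP median was longer in 28% or 54% of runs and otherwise equal.

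**The case against.** The case for the SAP is a fair one.

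- **Section 9.4.6.2 may be only a treatment-stopping rule.** It sits in a section on prohibited medication and gives no event date. The protocol's PFS and DOR definitions count progression or death, and the PFS objective cites RECIST 1.1. This reading is possible, but 9.5.1.3.2 weakens it: there, in the efficacy section, the protocol lets therapy define progression without a scan.
- **Other protocol text fits the SAP.** Sections 9.1, 9.3.3 and 9.5.1.4 list the start of another anticancer therapy separately from progression as a reason to end tumor assessments. This stands. The tension is partly inside the protocol.
- **The SAP's choice looks deliberate.** It cites FDA guidance, and the protocol leaves analytical detail to the SAP. That explains the choice but does not tell the reader that the protocol's wording was set aside.
- **The scopes differ.** Section 9.4.6.2 concerns therapy while on study and couples it with stopping study drug. The Table 1 row also takes in therapy begun after study drug was stopped for another reason. This stands: only part of the row is in clear conflict.
- **The stakes are limited.** These are descriptive, single-arm estimates with no test or threshold, and cohort decisions rest on confirmed responses. This also stands.

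A reader might go further and infer that the censoring is informative because these subjects are already deteriorating. That is plausible, since the protocol lets treatment stop for lack of clinical benefit in the investigator's opinion, but nothing in the documents establishes it.

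**Conclusion.** The point holds in a bounded form. For subjects who receive other antitumor therapy while on study, Protocol 9.4.6.2 and SAP Table 1 give opposite outcomes, and the SAP does not declare the difference. The SAP rule gives fewer PFS and DOR events, so medians are expected to be longer or unchanged.

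The size cannot be derived from the documents. The ratios of 1.11 and 1.25 are conditional on f = 10% and 20% and on constant, independent hazards. With about 4% of subjects affected, the median did not move in most simulated runs.

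Three stronger inferences are not supported. One is that the reported medians will certainly be inflated: small numbers often leave them unchanged. Another is that every subject in the Table 1 row is misclassified: the row is wider than the protocol sentence. The third is that the event rule must be primary: the protocol sentence supplies no date, and other protocol passages sit comfortably with censoring. The primary endpoint, confirmed objective response, is unaffected.

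**What to change.** 1. Reconcile Protocol 9.4.6.2 and 9.5.1.3.2 with SAP Table 1. State which rule is primary for PFS and for DOR and, if it is the event rule, the date of the event.
2. If censoring stays primary, list it in SAP section 7 as a departure from the protocol's wording.
3. In either case, run the other rule as a labelled sensitivity analysis for both endpoints.
4. Report how many subjects are affected, with on-study therapy separate from therapy started after study drug was stopped, and give both medians.

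The cost is one table row or one line in SAP section 7, plus one extra Kaplan-Meier run each for PFS and DOR. The medians may look less favourable under the protocol's rule.

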9.4.7 Treatment Compliance

Records of treatment compliance for each subject will be kept during the study. Clinical research associates (CRAs) will review treatment compliance during site visits and at the completion of the study.

9.4.8 Drug Supplies and Accountability

In compliance with local regulatory requirements, drug supplies will not be sent to the investigator until the following documentation has been received by the sponsor:

- A signed and dated confidentiality agreement.
- A copy of the final protocol signature page, signed and dated by both the sponsor and investigator.
- Written proof of approval of the protocol, the ICFs, and any other information provided to the subjects by the IRB/IEC for the institution where the study is to be conducted.

- A copy of the IRB/IEC-approved ICF and any other documentation provided to the subjects to be used in this study.
- The IRB/IEC membership list and statutes or Health and Human Services Assurance number.
- A copy of the certification and a table of the normal laboratory ranges for the reference laboratory conducting the clinical laboratory tests required by this protocol.
- An investigator-signed and dated FDA Form FDA 1572, where applicable.
- Financial Disclosure form(s) for the principal investigator (PI) and all subinvestigators listed on Form FDA 1572, where applicable.
- A signed and dated curriculum vitae (CV) of the PI including a copy of the PI's current medical license or medical registration number on the CV.
- A signed and dated clinical studies agreement.

The investigator and the study staff will be responsible for the accountability of all study drugs (dispensing, inventory, and record keeping) following the sponsor's instructions and adherence to Good Clinical Practice (GCP) guidelines as well as local or regional requirements.

Under no circumstances will the investigator allow the study drugs to be used other than as directed by this protocol. Study drugs will not be dispensed to any individual who is not enrolled in the study.

The site must maintain an accurate and timely record of the following: receipt of all study drugs, dispensing of study drugs to the subject, collection and reconciliation of unused study drugs that are either returned by the subjects or shipped to site but not dispensed to subjects, and return of reconciled study drugs to the sponsor or (where applicable) destruction of reconciled study drugs at the site. This includes, but may not be limited to: (a) documentation of receipt of study drugs, (b) study drugs dispensing/return reconciliation log, (c) study drugs accountability log, (d) all shipping service receipts, (e) documentation of returns to the sponsor, and (f) certificates of destruction for any destruction of study drugs/study supplies that occurs at the site. All forms will be provided by the sponsor. Any comparable forms that the site wishes to use must be approved by the sponsor.

The study drugs and inventory records must be made available, upon request, for inspection by a designated representative of the sponsor or a representative of a health authority (eg, FDA, Medicines and Healthcare Products Regulatory Agency [MHRA]). As applicable, all unused study drugs and empty and partially empty containers from used study drugs are to be returned to the investigator by the subject and, together with unused study drugs that were shipped to the site but not dispensed to subjects, are to be returned to the sponsor's designated central or local depot(s) during the study or at the conclusion of the study, unless provision is made by the sponsor for destruction of study drugs and containers at the site. Destruction at the site will only occur under circumstances where regulation or supply type prohibits the return of study drugs to the central or local depot(s). Approval for destruction to occur at the site must be provided by the sponsor in advance. Upon completion of drug

accountability and reconciliation procedures by the site's personnel and documentation procedures by the sponsor's personnel, study drugs that are to be returned to the sponsor's designated central or local depot(s) must be boxed, sealed, and shipped back to the central or local depot(s) following all local regulatory requirements. In some regions, study drugs may be removed from the site and hand delivered to the central or local depot by sponsor representatives. Where study drugs are approved for destruction at the site, destruction will occur following the site's standard procedures and certificates of destruction will be provided to the sponsor.

Drug accountability will be reviewed during site visits and at the completion of the study.

9.5 Study Assessments

9.5.1 Assessments

9.5.1.1 Demography

Subject demography information will be collected at the Screening Visit. Demography information includes date of birth (or age), sex, race/ethnicity.

9.5.1.2 Baseline Assessments

Baseline characteristics and assessments will be collected at the Screening Visit. End-of-Treatment assessments will be collected within 28 days of the last dose of study drug. Screening and Baseline characteristics and End-of-Treatment assessments are listed in the Schedule of Procedures/Assessments ([Table 9](#)).

9.5.1.2.1 MEDICAL HISTORY AND PHYSICAL EXAMINATIONS

Medical and surgical history and current medical conditions will be recorded at the Screening Visit. All medical and surgical history relating to anticancer treatment must be noted in the Medical History and Current Medical Conditions CRF.

Physical examinations (comprehensive or symptom directed) will be performed as designated in the Schedule of Procedures/Assessments ([Table 9](#)). A comprehensive physical examination will include evaluations of the head, eyes, ears, nose, throat, neck, chest (including heart and lungs), abdomen, limbs, skin, and at baseline, a complete neurological examination. On subsequent evaluations an assessment of neuropathy (neuropathy present/absent and CTC AE Grade) will be made as part of the physical examination. A urogenital examination will only be required in the presence of clinical symptoms related to this region. Documentation of the physical examination will be included in the source documentation at the site. Significant findings at the Screening Visit will be recorded on the Medical History and Current Medical Conditions CRF. Changes from screening physical examination findings that meet the definition of an AE will be recorded on the Adverse Events CRF.

